3.8. Visit Windows

3.8.1. Definition of Study Day

Study day is the day relative to the date of the first dose of study drug. Study Day 1 will be defined as the date of the first dose of study drug administration.

Study day will be calculated from the date of first dose of study drug and derived as follows:

- For postdose study days: Assessment Date – First Dose Date + 1
- For days prior to the first dose: Assessment Date – First Dose Date

The last dose date for an individual study drug will be the end date on the study drug administration eCRF for the record where the “subject permanently discontinued” flag is ‘Yes’. The last dose date will be defined as the maximum of the last dose dates of individual study drugs in a treatment group.

If there are subjects for whom the date of last study drug is unknown due to the reason that the subject was lost to follow-up and not able to be contacted, the date of last dose will be estimated using the maximum of nonmissing study drug start or stop dates, visit dates and laboratory collection dates (posttreatment visits and unscheduled visits are not included).

3.8.2. Analysis Windows

Subject visits might not occur on protocol-specified days. Therefore, for the purposes of analysis, observations will be assigned to analysis windows.

In general, the baseline value will be the last nonmissing value on or prior to the first dose date of study drug.

HCV RNA, vital signs, and safety laboratory data collected up to the last dose date + 3 days are considered to be on-treatment data and HCV RNA, vital signs, and safety laboratory data collected after the last dose date + 3 days are considered posttreatment data. The analysis windows for on-treatment HCV RNA, vital signs and safety laboratory data are provided in Table 3-1.

Table 3-1. Analysis Windows for On-treatment HCV RNA, Vital Signs and Safety Laboratory Data

Nominal Visit	SOF/VEL + RBV 12 Weeks			SOF/VEL + RBV 24 Weeks		
	Nominal Day	Lower Limit	Upper Limit	Nominal Day	Lower Limit	Upper Limit
Baseline	1	(none)	1	1	(none)	1
Week 1	7	2	11	7	2	11
Week 2	14	12	18	14	12	18
Week 3	21	19	25	21	19	25
Week 4	28	26	32	28	26	32
Week 5	35	33	39	35	33	39
Week 6	42	40	49	42	40	49
Week 8	56	50	63	56	50	63
Week 10	70	64	77	70	64	77
Week 12	84	78	≥ 85	84	78	98
Week 16	NA	NA	NA	112	99	126
Week 20	NA	NA	NA	140	127	154
Week 24	NA	NA	NA	168	155	≥ 169

HCV RNA, vital sign, and safety laboratory data collected after the last dose date + 3 days will be assigned to the posttreatment follow-up (FU) visit. Visit windows will be calculated from the last dose date (ie, FU Day = collection date minus the last dose date) as shown in Table 3-2.

Table 3-2. Analysis Windows for Posttreatment HCV RNA, Vital Signs and Safety Laboratory Data

Nominal FU ^a Visit	HCV RNA/Vital Sign			Vital Signs and Safety Laboratory Data ^b		
	Nominal FU Day	Lower Limit	Upper Limit	Nominal FU Day	Lower Limit	Upper Limit
FU-4	28	21	69	28	4	30
FU-12	84	70	146	NA	NA	NA
FU-24	168	147	210	NA	NA	NA

a FU-x visit = posttreatment Week-x follow-up visit.

b Vital signs and safety labs will only be summarized for the FU-4 visit (up to 30 days after last dose).

ECG data is collected at baseline only. Qualitative assessments of whether the ECG is normal or abnormal will be assessed at baseline.

3.8.3. Selection of Data in the Event of Multiple Records in an Analysis Window

Depending on the statistical analysis method, single values may be required for each analysis window. For example, change from baseline by visit usually requires a single value, whereas a time-to-event analysis would not require one value per analysis window.

If multiple valid nonmissing numeric observations exist in an analysis window and, a single value is needed, records will be chosen based on the following rules:

- For baseline, the last available record on or prior to the date of the first dose of study drug will be selected. If there are multiple records with the same time or no time recorded on the same day, the average (arithmetic mean) will be used for the baseline value. If multiple ECG measurements occur on the same day prior to first dose of any study drug, the average will be used as baseline value for continuous data, regardless of the timing of these multiple ECG measurements.
- For postbaseline visits:
 - The record closest to the nominal day for that visit will be selected except for HCV RNA posttreatment follow-up visits, for which the latest record in the analysis window will be selected.
 - If there are 2 records that are equidistant from the nominal day, the later record will be selected.
 - If there is more than 1 record on the selected day, the average will be taken, unless otherwise specified.

If multiple valid nonmissing categorical observations exist in a window, records will be selected as follows:

- For baseline, the last available record on or prior to the date of the first dose of study drug will be selected. If there are multiple records with the same time or no time recorded on the same day, the value with the lowest severity will be selected (eg, normal will be selected over abnormal). If multiple ECG measurements occur on the same day prior to first dose of any study drug, the value with the lowest severity will be selected regardless of the timing of these multiple ECG measurements.
- For postbaseline visits, follow the same rules described above for postbaseline numeric observations, except that if there are multiple records on the same day, the most conservative value will be selected (eg, abnormal will be selected over normal).

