6.3.2. Weeks 2 and 3 (\pm 3 days)

The following procedures/assessments are to be completed at the end of Weeks 2 and 3:

- Perform complete physical examination (refer to Section [6.7.3](#))
- Obtain weight
- Obtain vital signs (refer to Section [6.7.4](#))
- Assessment of AEs and concomitant medications
- Assess adherence with study drug dosing regimen including pill count
- Obtain blood samples for tests (approximately 35 mL of blood will be drawn for required tests):
 - Hematology
 - Chemistry
 - Coagulation tests
 - HCV RNA
 - Viral RNA Sequencing / Phenotyping Sample and/or HBV DNA Sample
 - Single PK sample
 - If applicable, collect intensive PK Substudy samples at either the Week 2, 3, or 4 visit (for subjects who have consented) (an additional 55mL of blood will be drawn)

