3.6. Missing Data and Outliers

3.6.1. Missing Data

In general, missing data will not be imputed unless methods for handling missing data are specified.

For missing last dosing date of study drug, imputation rules are described in Section 3.8.1. The handling of missing or incomplete dates for adverse event (AE) onset is described in Section 7.1.5.2, and for prior and concomitant medications in Section 7.4.

For analyses of categorical HCV RNA data, missing posttreatment HCV RNA data will have the missing data imputed. Missing on-treatment HCV RNA will have the missing data imputed up to the time of the last dose (for on-treatment displays). If the study day associated with the last

dosing date is greater than or equal to the lower bound of a visit window, and the value at the visit is missing, the value will be imputed. If the study day associated with the last dosing date is less than the lower bound of a visit window then the on-treatment value at that visit will remain missing.

If an HCV RNA data point is missing and is preceded and followed in time by values that are “< lower limit of quantitation (LLOQ) target not detected (TND),” then the missing data point will be set to “< LLOQ TND.” If a data point is missing and preceded and followed by values that are “< LLOQ detected,” or preceded by “< LLOQ detected” and followed by “< LLOQ TND,” or preceded by “< LLOQ TND” and followed by “< LLOQ detected,” then the missing value will be set to “< LLOQ detected.” In these situations the data point will be termed a bracketed success; otherwise, the data point will be termed a bracketed failure (ie, \geq LLOQ detected). If a data point is missing and is not bracketed, the missing data point will also be termed a failure (ie, \geq LLOQ detected) except for SVR24, which will be imputed according to SVR12 status. Success for SVR12 who have no further HCV RNA measurements collected will be counted as a success for SVR24 due to the high correlation between these 2 endpoints.

For the analyses of continuous HCV RNA efficacy data, when and only when a missing HCV RNA value is imputed as < LLOQ TND or < LLOQ detected according to the imputation rule described above, the corresponding continuous value will be imputed to LLOQ – 1 IU/mL. No other imputation will be performed for continuous HCV RNA data.

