4.2.1. Duration of Exposure to Study Drug

Total duration of exposure to study drug will be defined as last dose date – first dose date + 1, regardless of any temporary interruptions in study drug administration, and will be expressed in weeks using up to 1 decimal place (eg, 4.5 weeks).

The total duration of exposure to study drug will be summarized using descriptive statistics (n, mean, SD, median, Q1, Q3, minimum, and maximum) and the number and percentage of subjects (ie, cumulative counts) exposed through the following time periods: baseline (Day 1), Week 1 (Day 7), Week 2 (Day 14), Week 3 (Day 21), Week 4 (Day 28), Week 5 (Day 35), Week 6 (Day 42), Week 8 (Day 56), Week 10 (Day 70), Week 12 (Day 84), and for the 24-week arm only, Week 16 (Day 112), Week 20 (Day 140), and Week 24 (Day 168). A 3-day window will be applied to the last planned on-treatment visit to match with the protocol-specified visit window (ie, the number of subjects exposed through Week 12 or Week 24 will be calculated as the number of subjects who were exposed to study drug for at least 81 days or 165 days, respectively). Summaries will be provided by treatment group for the Safety Analysis Set.

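### In SAP Table 3-1 the nominal days and the Week 1-6 window limits follow conventions one day apart, so on the SAP's own nominal days a compliant early visit at Weeks 2-6 is filed under the previous week

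*SAP*

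**What the plan says.** SAP 3.8.1 makes the first-dose date Study Day 1 and counts forward from it: "For postdose study days: Assessment Date – First Dose Date + 1".

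SAP 3.8.2, Table 3-1, gives each visit a nominal day, a lower limit and an upper limit, identical in the two arms up to Week 10. Three rows show the pattern: "Week 1 7 2 11 7 2 11", "Week 2 14 12 18 14 12 18" and "Week 3 21 19 25 21 19 25". Weeks 4, 5 and 6 have nominal Days 28, 35 and 42 with windows 26-32, 33-39 and 40-49.

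Protocol 6.3 allows 3 days either side of each on-treatment visit and places visits at the end of a week, without a study-day number. Section 6.3.2 is typical: "The following procedures/assessments are to be completed at the end of Weeks 2 and 3".

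Three further rules matter:
- If a window holds several records, SAP 3.8.3 says "The record closest to the nominal day for that visit will be selected" (posttreatment HCV RNA excepted), with ties going to the later record.
- If an on-treatment categorical HCV RNA value is missing, SAP 3.6.1 counts it a success when the values on both sides are < LLOQ; "otherwise, the data point will be termed a bracketed failure". An unbracketed missing value is also a failure.
- SAP 6.2.2 excludes a missing continuous HCV RNA value unless it is bracketed by results < LLOQ. Missing laboratory and vital-sign values are not imputed (Protocol 8.3).

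**The concern.** A window is meant to hold every visit that the protocol permits for that week. For Weeks 2-5 the printed windows run from 2 days before the nominal day to 4 days after it, and Week 6 also opens 2 days before. The earliest permitted day therefore lies outside its own window and inside the previous week's.

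Two on-treatment records then compete for one window and the next window may hold none. The percentage with HCV RNA < LLOQ by visit is a secondary endpoint (SAP 6.2.1), and the early weeks are when subjects cross the LLOQ. That is where a preceding value still at or above LLOQ would turn an emptied week into an imputed failure although the subject's sample was < LLOQ. By-visit laboratory values and vital signs use the same windows and would lose that week's value.

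**Working it through.** **1. Permitted days against windows, using the printed nominal day N.** Permitted days are N - 3 to N + 3.

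| Visit | N | Permitted | Table 3-1 window | Outside own window | Filed under |
|---|---|---|---|---|---|
| Week 1 | 7 | 4-10 | 2-11 | none | - |
| Week 2 | 14 | 11-17 | 12-18 | 11 | Week 1 |
| Week 3 | 21 | 18-24 | 19-25 | 18 | Week 2 |
| Week 4 | 28 | 25-31 | 26-32 | 25 | Week 3 |
| Week 5 | 35 | 32-38 | 33-39 | 32 | Week 4 |
| Week 6 | 42 | 39-45 | 40-49 | 39 | Week 5 |

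From Week 8 on, every permitted day falls in its own window (for example 53-59 within 50-63).

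**2. Which days do the limits belong to?** Rebuild each boundary as the midpoint between consecutive visit days.
- Days 7k (7, 14, 21, ...): the Week 1/2 midpoint is (7 + 14)/2 = 10.5, giving Week 1 = 2-10 and Week 2 = 11-17. Continuing gives 18-24, 25-31, 32-38 and 39-49. With ties to the earlier visit this reproduces Week 8 onward but none of the Week 1-6 rows.
- Days 7k+1 (8, 15, 22, ...): the midpoint is (8 + 15)/2 = 11.5, giving Week 1 = 2-11 and Week 2 = 12-18. With ties to the later visit this reproduces every row.

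So the limits follow 7k+1 and the nominal-day column follows 7k.

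**3. What happens to a displaced visit (7k reading).** Put the index visit on its earliest day and let the previous and next visits each take any of 7 permitted days: 7 x 7 = 49 combinations.
- Weeks 2-5: the next visit lands in the index window only if it too is on its earliest day, which is 7 x 1 = 7 combinations. The window is empty in 7 x 6 = 42. In the other 7 it holds the next visit's value, mislabelled.
- Week 6: the next visit is no earlier than Day 53 and the window closes at Day 49, so it is empty in 49 of 49.
- The displaced record is never chosen for Week 1. For Weeks 2-5 it is chosen for the previous week only when that week's own visit was also displaced (7 of 49).

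**4. Example.** Week 2 on Day 14 (at or above LLOQ), Week 3 on Day 18 (< LLOQ), Week 4 on Day 28 (< LLOQ); all are compliant. Days 14 and 18 both file under Week 2, and Day 14 is kept (distance 0 against 4). Week 3 is empty and preceded by a value at or above LLOQ, so it is imputed as a failure.

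**5. Illustrative size (assumed timing, not in the documents).** The share with an empty own week is P(earliest day) x P(next visit not on its earliest day); for Week 6 the second factor is 1.
- Even spread over 7 days: 1/7 x 6/7 = 12.2% for Weeks 2-5 and 1/7 = 14.3% for Week 6, or about 13 to 16 of 110 subjects per visit.
- Clustered on the nominal day (weights 1-2-3-4-3-2-1, total 16): 1/16 x 15/16 = 5.9% and 1/16 = 6.3%, or about 6 to 7 of 110.

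Assume also a lognormal time to < LLOQ with median 17 days and 89% by Day 28. Simulation then puts the fall in the reported percentage < LLOQ at about 0.5 to 0.6 points at Week 2, 1.2 to 1.7 at Week 3 and 0.6 to 1.0 at Week 4. The 89% is set near the Week 4 figures of 88.5% and 90.2% in Protocol 1.2.3.1.4 and 1.2.3.2.4, which come from other trials in other populations.

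**The case against.** The strongest answer is that no compliant visit need be misfiled. The protocol gives no study-day number. Because first dose is Day 1, a visit 7k days later falls on Study Day 7k+1. Permitted days for Weeks 2-6 are then 12-18, 19-25, 26-32, 33-39 and 40-46, and all fit the printed limits. The limits were evidently built that way, and the open-ended upper entries at 85 and 169 are also 7k+1 values. This stands as a real possibility, so a reader who infers that compliant visits are certainly being lost goes further than the documents allow. It does not rescue the table. The nominal-day column would then be the wrong part, and SAP 3.8.3 selects records by that column. With records on Days 13 and 16 in the Week 2 window, nominal Day 14 selects Day 13, whereas Day 15 would select Day 16.

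A reader might also take SAP 4.2.1 as proof that visits fall on Days 7k, since it lists "Week 1 (Day 7), Week 2 (Day 14), Week 3 (Day 21), Week 4 (Day 28" and subtracts 3 days from Days 84 and 168. That section is consistent with 7k but does not settle the matter. It measures exposure, and 84 or 168 once-daily tablets (SAP 4.2.2) span 84 or 168 days however visits are numbered.

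The reach is limited too:
- SVR4, SVR12 and SVR24 use the posttreatment windows of Table 3-2.
- On-treatment HCV RNA by visit is descriptive, and SAP 3.5 rules out any between-arm comparison.
- It would be wrong to say that hemoglobin results are lost. Counts below 10 and 8.5 g/dL at any postbaseline visit, treatment-emergent abnormalities and worst grades (SAP 7.2.1, 7.2.2) do not depend on these windows, and all results are listed.
- For scale, at 40/45 (89%) the planned 95% Clopper-Pearson interval is about 76% to 96%, far wider than the illustrative shift.

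All of these limits stand.

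**Conclusion.** The two columns of Table 3-1 disagree by one day for Weeks 1-6, and the table is wrong as written on either reading. On the SAP's stated nominal days, one of seven permitted days is misfiled at each of five visits (Weeks 2-6). On the 7k+1 reading nothing compliant is misfiled, but closest-to-nominal selection works from the wrong day.

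The consequence is confined to by-visit on-treatment HCV RNA, laboratory values and vital signs. The documents do not give the share of visits on the earliest day. It could be near zero, and the 6% to 14% range and the shifts of up to about 1.7 points are illustrations only. The imputed-failure mechanism assumes that the neighbouring values in the bracketing rule are the values selected for the adjacent visits. SAP 6.2.2 implies this by assigning one value per visit and then imputing, but SAP 3.6.1 does not say so outright.

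This is a correction worth making, not a threat to the primary result.

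**What to change.** First confirm from the scheduling instructions, or from the visit dates, whether visits were planned on Study Day 7k or 7k+1. Then align the columns in both arms:
- **Visits on Day 7k, as the SAP states:** change ten limits per arm. Week 1 upper becomes 10; Weeks 2-5 become 11-17, 18-24, 25-31 and 32-38; Week 6 lower becomes 39. Leave Week 8 onward alone. Every permitted day then falls in its own week.
- **Visits on Day 7k+1:** keep the limits and change the nominal-day column to 8, 15, 22 and so on through the last visit.

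The order matters. If visits are really on 7k+1, the narrower limits would misfile the latest permitted day at Weeks 1-5 (Days 11, 18, 25, 32 and 39). Leave the exposure thresholds in SAP 4.2.1 unchanged in both cases.

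The cost is a table edit and the matching program change before database finalization, with no new data.

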4. SUBJECT DISPOSITION

4.1. Subject Enrollment and Disposition

A summary of subject enrollment will be provided for each investigator within Japan by treatment group and total. The summary will present the number and percentage of subjects in the Safety Analysis Set. For each column, the denominator for the percentage calculation will be the total number of subjects analyzed for that column.

A similar randomization table will be provided by randomization stratum for each treatment group and total. The denominator for the percentage of subjects in the stratum will be the total number of subjects in the Safety Analysis Set within that stratum for each treatment group and total. If there are discrepancies in the value used for stratification assignment between the Interactive Web Response System (IWRS) and the clinical database including CRF and laboratory data, the value collected in the clinical database will be used for the summary. A listing of subjects with the IWRS randomization strata that differ from stratification factor data entered in the clinical database at the time of data finalization will be provided.

The randomization schedule used for the study will be provided as an appendix to the CSR.

A summary of subject disposition will be provided by treatment group and total. This summary will present the number of subjects screened, the number of subjects not randomized, the number of subjects randomized, the number of subjects randomized but never treated, randomized and treated (ie, safety analysis set), FAS, PK analysis set, and the number and percentage of subjects in each of the categories listed below. For the “Treated” category, the denominator for the percentage calculation will be the total number of subjects randomized for each column. For all other categories, the denominator for the percentage calculation will be the total number of subjects in the Safety Analysis Set for each column:

- Completed study treatment
- Did not complete study treatment (with reasons for premature discontinuation of study treatment)
- Completed study
- Did not complete study (with reason for premature discontinuation of study)

Among subjects who completed study treatment and who discontinued study treatment, the number and percentage of subjects will be summarized for:

- Who had no HCV posttreatment Week 4 assessment and thereafter (No HCV FU-4 and thereafter)
- Who had HCV posttreatment Week 4 assessment but no HCV posttreatment Week 12 and thereafter (With HCV FU-4 but No FU-12 and thereafter)

If a subject did not have any HCV RNA assessment \geq 21 days after the last dose of any study drug (ie, lower bound of FU-4 visit for HCV RNA data), the subject is categorized as having “No HCV FU-4 and thereafter.” If a subject had the HCV FU-4 assessment but did not have any HCV RNA assessment \geq 70 days after the last dose of any study drug (ie, lower bound of FU-12 visit for HCV RNA data), the subject is categorized as having “With HCV FU-4 but No FU-12 and thereafter.”

In addition, the total number of subjects who were randomized, and the number of subjects in each of the disposition categories listed above will be depicted by a flowchart.

The following by-subject listings will be provided by subject identification (ID) number in ascending order to support the above summary tables:

- Disposition for subjects who complete study treatment and study
- Disposition for subjects who did not complete study treatment and/or study with reasons for premature discontinuation of study treatment and/or study
- Lot number and kit ID (if applicable)

4.2. Extent of Exposure

Extent of exposure to study drug will be examined by assessing the total duration of study drug exposure and the level of adherence to the study drug regimen as specified in the study protocol.

4.2.1. Duration of Exposure to Study Drug

Total duration of exposure to study drug will be defined as last dose date – first dose date + 1, regardless of any temporary interruptions in study drug administration, and will be expressed in weeks using up to 1 decimal place (eg, 4.5 weeks).

The total duration of exposure to study drug will be summarized using descriptive statistics (n, mean, SD, median, Q1, Q3, minimum, and maximum) and the number and percentage of subjects (ie, cumulative counts) exposed through the following time periods: baseline (Day 1), Week 1 (Day 7), Week 2 (Day 14), Week 3 (Day 21), Week 4 (Day 28), Week 5 (Day 35), Week 6 (Day 42), Week 8 (Day 56), Week 10 (Day 70), Week 12 (Day 84), and for the 24-week arm only, Week 16 (Day 112), Week 20 (Day 140), and Week 24 (Day 168). A 3-day window will be applied to the last planned on-treatment visit to match with the protocol-specified visit window (ie, the number of subjects exposed through Week 12 or Week 24 will be calculated as the number of subjects who were exposed to study drug for at least 81 days or 165 days, respectively). Summaries will be provided by treatment group for the Safety Analysis Set.

